## 5.6 RECRUITMENT PLAN FOR PROSPECTIVE STUDIES

**Table 5** – Recruitment plan including estimated number of eligible patients, total number of participants expected to be approached or screened via the study kiosk and online data capture tool.

Recruitment Plan	
Estimated number of potentially eligible study participants, from prior research and examining medical records: ~400 eligible patients at OSU, UIC and Duke, Hopkins ~200 eligible at Pitt	1600 at clinical sites
Our community-based organizations reach 10000+ patients. Conservative estimate is that 50% of those are eligible adults with chronic pain	5000 through CBO networks
Total number of study participants expected to be approached in clinic (n = 450) or complete online screener (n = 100)	550
Of those screened, total number of study participants expected to be eligible	450
Of those eligible, total number participants enrolled via clinics (n = 300) and CBOs online (n = 50)	350
Target sample size	350
Total number of clinical sites that will enroll participants	5
Projected rate of enrollment	Month 7 start of enrollment
Estimated percentage of participant dropout	10-15% complete no follow-up assessments 30-40% stop using intervention before reaching Module 4

**Table 6.** Estimated final racial/ethnic and gender enrollment table (N = 350)

Race	Male (N)	Female (N)	Total (N)
American Indian/ Alaska Native			
Asian			
Black/African American	170	170	340
Hawaiian/Pacific Islander			
White			
Multirace	5	5	10
Ethnicity	Male (N)	Female (N)	Total (N)
Hispanic (Latino/Latina)			
Non-Hispanic	175	175	350

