Each of the 350 patients recruited will be asked to complete all modules in one of two programs within the Internet-delivered CaRISMA pain intervention: cCBT or m-Education. Participants will only have access to the content that is relevant to their assigned program, which they will be randomized into when they open the CaRISMA intervention for the first time. In addition to completing the modules, participants will also be asked to have weekly check-ins (via phone or text) with their assigned health coach during the first 12 weeks of the intervention when modules are being completed. Participants will log a daily pain diary within the intervention throughout the entire year of the study. The pain diary feature will prevent participant recall or memory bias, which will provide the study team with the most accurate data to track each participant's health outcomes while using the CaRISMA intervention.

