#### 6.1.2 ADMINISTRATION AND/OR DOSING

For at least 12 weeks, one group will be asked to engage in a mobile cCBT program tailored for adults with SCD, which mimics the behavioral services SCD patients would receive when working with a psychologist or behavioral pain specialist. The second group will receive pain and SCD education on their mobile phones (m-Education). The CaRISMA intervention, which delivers both cCBT and m-Education programs, is accessed on a smartphone and is made up of **four** primary components:

- 1) Chatbot and Health Coach Messaging. Using artificial intelligence (AI) similar to Alexa or Siri, we provide 24/7 chat style interactions to assess needs and deliver personalized content to the user. The chatbot goes beyond text messages, using graphical interfaces, widgets, and videos to provide lessons, quizzes,

quick coping tools, and occasional entertainment. Periodically and upon request, our health coaches will send personalized messages via text message or through the chatbot platform.

- 2) **Toolbox and Badges.** As users go through the lessons via the chatbot, they can view their progress and gain access to all the lessons and tools they have unlocked. This is where they can also view status badges they received for specific accomplishments.
- 3) **Pain Diary.** Users will record their pain, mood, and medications used daily on the CaRISMA intervention. They can also view trends in their pain/mood data.
- 4) **Social.** The intervention encourages users to visit CBO social media groups and live meetups run by our CBO partners. Access to outside social support will not be monitored or recorded.

Through interacting with the chatbot, study participants will view video lessons and answer quiz questions to verify understanding of the material. If a quiz question is answered incorrectly, the chatbot will provide the correct answer to clear up any misunderstanding of the material. The chatbot has been programmed by study staff to allow content to be tailored for each participant's needs. Participants are asked personalized questions in between video lessons to aid in transferring the learned techniques to real-world application. Participants interested in learning more are also given the option to view extra, topic-specific content.

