### Dropout

Dropout concerns the number of patients choosing to end treatment prematurely. Early termination can be related to deterioration of target symptoms, nonresponse, and/or experiencing adverse events, presumably related to treatment, e.g., increase in symptom severity, or demoralization. It may also be that dropout was related to a decrease in symptom severity, i.e., some patients might experience relief after a short period of time, perceiving more treatment as redundant. When feasible, we will make every effort to contact participants by phone and/or electronic survey to determine the reason for dropout or discontinuation of the intervention.

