Sample Size Calculation. For the primary test of comparative effectiveness of digital CBT versus mobile education (m-Education) for the trial, the power calculation is based on the comparison of intervention groups for the main outcome of the 6-month change in pain interference. Specifically, our sample size of 350 participants enables 80% power to detect a difference of 0.37 SDs between study arms on 6-month changes. This detectable effect is also applicable to key secondary outcomes, such as pain intensity and depression, as measured by the PHQ-9. Our calculations account for 15% attrition at 6 months.

Hypotheses. Our study hypotheses are:

H1: cCBT will confer greater benefit on pain outcomes at 6 months, compared to m-Education. The primary outcome of the proposed trial is change in pain interference at 6 months. The main secondary outcome will be change in average weekly pain intensity. We will also explore sustainability of the intervention effects at 12 months.

H2: cCBT will confer greater benefit on depressive symptoms at 6 months, compared to m-Education.

H3: cCBT will confer greater decreases in health care utilization (opioid prescriptions, acute care visits) and opioid misuse behaviors (Current Opioid Misuse Measure – COMM) over 12 months, compared to m-Education.

Analysis Sets. All analyses will be under the framework of intention-to-treat, such that all randomized participants are included regardless of initiation or adherence to interventions. However, we will conduct sensitivity analyses restricting to participants who were randomized with confirmation of sickle cell disease.

Study Outcomes.

Primary Pain Outcome: Pain Interference

Patient Reported Outcomes Measurement Information System Pain Interference assesses the effect of patient-reported pain on relevant aspects of a person's life and may include the extent to which pain hinders engagement with social, cognitive, emotional, physical, and recreational activities. This measure will only be completed at baseline and 3, 6, and 12 months.

Secondary Pain Outcome: Daily Pain Intensity

Participants will be asked to enter their daily pain via a mobile website. They will receive reminder notifications via text messages for 2-week periods at baseline and 3, 6, and 12 months. However, between these automated-reminder periods, participants will be encouraged to continue entering their pain scores on the mobile pain web app.

Other Secondary Outcomes

Painimation

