Linear mixed models will be employed for the primary outcome of pain interference as a function of time, study arm (digital CBT vs Education), time \times study arm interaction, study site, and baseline depression level (PHQ-9 \leq 10 vs PHQ-9 $>$ 10). We will account for multiple observations for each participant by including a random effect for the subject. In addition, baseline variables with large, clinically meaningful between-arm differences will be included as covariates in the secondary analyses. Contrasts will be estimated to assess the impact of digital CBT and education intervention on 6-month improvements in pain interference. As a secondary investigation, we will use the same linear mixed models to address whether the 6-month improvements are sustainable for 12 months. The analytic strategy for the key secondary outcome of pain intensity will be identical to that of the primary outcome. As the confirmation of a sickle cell diagnosis may not be made immediately after randomization, we will conduct an a priori sensitivity analysis restricting eligible participants with the confirmation of SCD.

Analysis of Secondary Outcomes

Secondary outcomes such as PHQ-9, Current Opioid Misuse Measure, GAD-7, Adult Sickle Cell Quality of Life Measurement Information System, and SCSES will be analyzed using similar linear mixed models with time, study arm, time×study arm interaction, study site, and baseline depression level as fixed covariates and a random effect for each subject. Health care use will be compared between study arms using generalized linear models to account for count data (i.e., Poisson regression) for each of the following: the number of opioid prescriptions, number of emergency department visits, and number of hospitalizations over 12 months after study entry. Predictors will include the study arm, study site, and baseline depression level. The corresponding health care use in the 12 months before study entry will be entered as a covariate in each model. We will offset each model by the participant's time in the study.

Subgroup Analysis

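### The SAP's pain-intensity analysis depends on continued diary entry and makes no use of the survey interference scores that people who stop the diary may still give

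*SAP*

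**What the plan says.** **Where each outcome comes from.** In Protocol 4.1, PROMIS Pain Interference and the PHQ-9 are completed through an online survey link sent by text or email. Table 4 there gives the mobile app as the source of daily pain intensity. Protocol 6.1.1 says: "Participants will log a daily pain diary within the intervention throughout the entire year of the study". Protocol 6.1.2 lists the diary among the four components of the intervention: "Users will record their pain, mood, and medications used daily on the CaRISMA intervention". The SAP (Secondary Pain Outcome) describes entry through a mobile website, with text reminders over two weeks at baseline and at 3, 6 and 12 months.

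**Expected loss.** Table 5 in Protocol 5.6 gives two separate rates: 10-15% with no follow-up assessment at all, and "30-40% stop using intervention before reaching Module 4". On the reasons for stopping, Protocol 8.3 (Dropout) names worsening and non-response, and adds: "It may also be that dropout was related to a decrease in symptom severity".

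**Power.** The SAP (Sample Size Calculation) says: "our sample size of 350 participants enables 80% power to detect a difference of 0.37 SDs between study arms on 6-month changes", and "Our calculations account for 15% attrition at 6 months". It extends this to intensity: "This detectable effect is also applicable to key secondary outcomes, such as pain intensity and depression, as measured by the PHQ-9".

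**Analysis.** The SAP (Analysis of Primary and Secondary Pain Outcomes) says: "The analytic strategy for the key secondary outcome of pain intensity will be identical to that of the primary outcome". Its Handling of Missing Values section is one general plan for all outcomes. It gives no expected diary completion and no minimum number of entries for a 6-month score.

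**The concern.** The two pain outcomes can be lost in different ways. Someone who stops using the program still receives the survey link, so interference can be observed. Intensity needs that person to keep making diary entries. Several provisions protect the survey more than the diary. Follow-up payments are for questionnaires (Protocol 5.6), a missed follow-up is defined by questionnaires (7.3), pain interference has priority for those who discontinue (7.2), and scheduled coach check-ins end at 12 weeks (4.1).

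A mixed model of intensity alone sees only the diary. For a person who stopped early, that is little beyond the baseline entries, even if the same person reported interference at 3 and 6 months. Stopping is disengagement from content that differs by arm, and the protocol expects it to be linked to symptom change in either direction. If that link differs between arms, the 6-month contrast is biased, and the observed variable most informative about the missing value is left out.

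The outcome matters. It is the key secondary outcome in the SAP, and the protocol calls it primary in sections 2.2, 4.1 (H1), 9.2 and 9.4.2.

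**Working it through.** **1. Inputs.** N = 350 at 1:1, 0.37 SD, 80% power and 15% attrition (SAP). Two-sided 0.05 is stated only for the interaction tests (Protocol 9.4.6) and is assumed here for the power statement. The 30-40% is from Protocol Table 5.

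**2. The plan's own figure.** For two means with SD = 1, n per arm = 2(1.960 + 0.842)² / 0.37² = 114.7, so 115. With 15% attrition, 115 / 0.85 = 135.3, so 136 per arm and 272 in total, not 350. With 350 randomised and 15% lost, 148.75 per arm remain. The detectable difference is then 2.802 × √(2/148.75) = 0.325 SD, and power at 0.37 SD is 89%. The stated 80% is not reproduced at this alpha. It is conservative: 80% needs 230 evaluable participants, and 1 − 230/350 = 34% loss.

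**3. Power for intensity at greater loss.** Power = Φ(0.37√(n/2) − 1.960), with n = 175(1 − loss) per arm:

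| Loss of 6-month intensity | n per arm | Power at 0.37 SD | Detectable at 80% |
|---|---|---|---|
| 15% | 148.75 | 89.1% | 0.325 SD |
| 22.5% (half of the stoppers beyond 15%, at 30%) | 135.6 | 86.1% | 0.340 SD |
| 27.5% (the same, at 40%) | 126.9 | 83.8% | 0.352 SD |
| 30% | 122.5 | 82.5% | 0.358 SD |
| 40% | 105 | 76.5% | 0.387 SD |
| 49% (15% and 40% compounding: 1 − 0.85 × 0.60) | 89.25 | 69.6% | 0.419 SD |

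A noncentral t calculation gives the same to within about half a point. The 30-40% range gives 0.358-0.387 SD, which brackets the stated 0.37.

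**4. Who could be recovered.** Suppose, as an upper limit, that everyone who stops the intervention also stops the diary, and that the 15% with no survey are all among them. Then 30 − 15 = 15% to 40 − 15 = 25% of 350, about 53 to 88 people, would have a 6-month interference score and no intensity score. The planned model uses none of those interference scores for intensity. The true number depends on diary completion, which neither document gives.

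**5. Possible size of bias.** A simulation used these assumptions, none of them from the documents:
- 175 per arm, normal outcomes and no true effect;
- 6-month diary missing in 30% or 40%, and survey missing in 15%, all among the stoppers;
- odds of stopping 1.5 times higher per SD of worsening in one arm, and unrelated to change in the other;
- correlation over time 0.5-0.6, and between intensity and interference 0.5-0.7.

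The single-outcome analysis was biased by 0.08-0.12 SD, against a standard error of 0.11-0.13, which is about 0.7-0.9 of a standard error. Adding baseline and 6-month interference left 0.056-0.098 SD, a reduction of about 15-36%. Supplying the 3-month survey scores as well, with early stoppers losing their 3-month diary, gave about 14-35%. When stopping was unrelated to change, variance fell by about 2-12%.

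**The case against.** **Strongest reply: the 30-40% does not measure diary loss.** It marks progress through the modules. The later SAP has pain entered on a mobile website with text prompts around month 6. Coaches contact people who miss pain entries (Protocol 4.1 and 6.4), and those who discontinue are encouraged to complete remaining assessments (7.2). All of this stands. A reader might infer that 30-40% will lack a 6-month score, which is two (30/15) to nearly three (40/15) times the attrition assumed. The documents do not say so. They support only that intensity may be missing more often than the survey outcomes. The reply does not settle the matter, because the SAP also calls the website a web app, does not separate it from the intervention, and supplies no value for those who never return to it.

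**Power.** A reader might also infer that the power statement is wrong for intensity. At two-sided 0.05 it is not, because the slack in the 0.37 SD figure absorbs most of the 30-40% range. Only a stricter alpha would change this. At 0.05/3, which no document states, power would be about 69% at 30% loss and 61% at 40%.

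**Missing data are already covered.** The SAP names joint or shared-parameter models if missingness is judged non-ignorable, and the protocol adds a dropout analysis (6.3). A likelihood-based model for a secondary outcome is defensible. However, the SAP would choose the fallback by comparing missingness rates between arms and baseline characteristics, and those comparisons cannot tell missing at random from missing not at random. Neither route is said to use interference to inform missing intensity.

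**The gain is partial.** This stands. The bias figures rest on chosen assumptions, and most of the bias remains. Painimation, which is in the same survey and can be adjusted for pain intensity, also carries information, but the plan does not use it for this purpose either.

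**Conclusion.** The point holds as a gap in the analysis of the key secondary outcome. Intensity depends on continued diary entry, missing scores may be linked to arm and symptom change, and the planned model ignores survey scores that the trial already collects from the same people.

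The power consequence is minor and the stated 0.37 SD needs no change, given two-sided 0.05. The bias consequence is of unknown size. The illustration of 0.08-0.12 SD shows what outcome-related stopping in one arm could do and is not a prediction. Under those assumptions, using interference removes about 15-35% of the bias and from a few percent to about 12% of the variance. How much it helps in practice depends on how many people stop the diary but answer the survey, and on the correlation between the two outcomes. Neither figure is in the documents.

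**What to change.** In the SAP section on the primary and secondary pain outcomes, replace the identical strategy for pain intensity with one of two prespecified main analyses:

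- multiple imputation of intensity, done separately by arm, with the baseline, 3-, 6- and 12-month survey interference scores in the imputation model alongside the observed diary data and the covariates of the analysis model; or
- an equivalent bivariate mixed model of intensity and interference.

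Keep the single-outcome mixed model as a sensitivity analysis. The sample size text can stay as it is.

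The cost is some SAP wording and modest extra analysis, with no new data collection. The limit should be stated with the change: it uses observed information better, but it does not remove bias from data missing not at random.

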### 6.4 STUDY INTERVENTION/EXPERIMENTAL MANIPULATION ADHERENCE

The major assumption is that patients will complete the intervention program to which they are randomly assigned. Although we have implemented several methods to promote engagement and limit dropout (e.g., health coaches), digital interventions often experience high attrition over time with few participants completing all assigned modules. We will track the reasons for noncompletion and seek patterns (e.g., moved away, died, started working and became too busy, people with higher cognitive level lost interest) that are amenable to statistical analysis of the missing data.

We will have monthly study retention meetings led by [name] and [name] to discuss recruitment, retention, and engagement at all sites. The health coaches will report to [name] and the study PIs if they are having difficulty contacting any participant on the study. [name] will also visit the health coaches at the University of Pittsburgh and the study staff at each clinical site to teach them how to work effectively with this patient population. She will occasionally visit with the health coaches at the University of Pittsburgh for booster sessions.

[name] will train health coaches on how to keep track of each participant's progress throughout the intervention. Each participant will be required to complete all modules, as well as weekly health coach check-ins during the first 12 weeks, and daily pain diaries throughout the 12 months of the study. In addition, participants will also be required to complete Painimation, , the SCSES, PROMIS, ASCQ-ME, PHQ-9, and GAD-7 questionnaires at baseline, 3-, 6-, and 12-month time points, as well as the COMM at baseline and 12-month follow-up. Failure to complete any of these will prompt health coaches to reach out via text message or phone to encourage participants to complete missing items. The qualitative interview delivered by Qual EASE is the only optional activity in the intervention. Since only 48 of the 350 participants will be selected for interview, any participant that opts out will be replaced by another participant, of those not previously selected.

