### 7.2 PARTICIPANT DISCONTINUATION/WITHDRAWAL FROM THE STUDY

A participant may be discontinued from study treatment at any time if the participant or the investigator feels that it is not in the participant's best interest to continue. The following is a list of possible reasons for study treatment discontinuation:

- Participant withdrawal of consent (or assent)
- Participant is not compliant with study procedures
- Adverse event that in the opinion of the investigator would be in the best interest of the participant to discontinue study treatment
- Protocol violation requiring discontinuation of study treatment
- Lost to follow-up

If a participant is withdrawn from treatment due to an adverse event, the participant will be followed and treated by the investigator until the abnormal parameter or symptom has resolved or stabilized.

All participants who discontinue study treatment should come in for an early discontinuation visit as soon as possible and will be encouraged to complete all remaining scheduled assessments (Pain Interference measure will be prioritized).

All participants are free to withdraw from participation at any time, for any reason, specified or unspecified, and without prejudice.

Reasonable attempts will be made by the investigator to ascertain a reason for participant withdrawals. The reason for the participant's withdrawal from the study will be specified in the participant's source documents.

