The ASCQ-ME emotional functioning and social impact quality-of-life measure was specifically designed for SCD and evaluates the health care experience of patients with SCD, emotional response to stress, and social relationships. These measures will only be completed at baseline and 3, 6, and 12 months.

Sickle Cell Self-Efficacy Scale

SCSES is a self-report measure to assess the ability of patients with SCD to function on a day-to-day basis and manage their SCD symptoms. This measure will only be completed at baseline and 3, 6, and 12 months.

Handling of Missing Values. We will minimize missing data by using an electronic data collection system and by contacting participants when data are not entered in a timely fashion. We will attempt to characterize the missingness mechanism (missing completely at random, missing at random, or not missing at random) by comparing rates of missingness or attrition between study arms. In addition, we will compare baseline characteristics between participants with and without missing outcome data. If we conclude that our missingness is random, then our likelihood-based approach for the primary analyses will address this. Otherwise, if the missingness can be characterized as nonignorable (not missing at random), we will use approaches such as joint modeling or shared parameter models to produce unbiased estimates of treatment effects. All reasons for dropout or other missing values will be entered by the research staff or community groups (if encountering the patient during community activities) and will be tabulated and summarized, and results will be reported using the CONSORT (Consolidated Standards of Reporting Trials) diagram. Patients who stop reporting data in the app will receive inquiry text messages or phone calls.

Statistical Analyses. All primary and secondary analyses will be preceded by descriptive analyses of the baseline and clinical characteristics. Summary statistics will include means and SDs for continuous variables and sample proportions for categorical variables. Median and IQR values will accompany nonnormal, continuous variables. The results will be presented both within and across study arms. All analyses will follow the intention-to-treat approach.

Analysis of Primary and Secondary Pain Outcomes

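### The checks that decide whether the mixed model stands cannot tell MAR from MNAR, and no MNAR sensitivity analysis is certain to run

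*SAP*

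**What the plan says.** The SAP, under Handling of Missing Values, will try to label missingness as completely at random, at random or not at random. It will do this "by comparing rates of missingness or attrition between study arms", and in addition "we will compare baseline characteristics between participants with and without missing outcome data". A two-way rule follows. On one branch, "If we conclude that our missingness is random, then our likelihood-based approach for the primary analyses will address this". On the other, where missingness is characterized as nonignorable, "we will use approaches such as joint modeling or shared parameter models to produce unbiased estimates of treatment effects". Protocol 7.3 and 9.4.5 carry the same rule.

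The analysis section of the SAP attaches no such condition: "Linear mixed models will be employed for the primary outcome of pain interference", with a random effect for subject. The SAP's only a priori sensitivity analysis restricts the sample to participants with confirmed sickle cell disease.

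On the expected amount of missing data, the SAP says "Our calculations account for 15% attrition at 6 months". Protocol Table 5 expects 10-15% of participants to complete no follow-up assessment. Protocol 7.2 says that participants who stop treatment "will be encouraged to complete all remaining scheduled assessments (Pain Interference measure will be prioritized". Protocol 6.3 promises a dropout analysis without a method. Protocol 6.4 will look for patterns in the reasons for noncompletion "that are amenable to statistical analysis of the missing data", but does not say how they enter the treatment-effect analysis.

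**The concern.** MAR and MNAR differ in whether, given everything observed, the chance of being missing still depends on the value that was not seen. Both planned comparisons use observed quantities only. Similar attrition and similar baselines therefore do not support the mixed model, and an imbalance in either does not show MNAR.

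The rule nevertheless carries weight. The documents give no criterion for the decision, leave the fallback model open, and do not say whether it replaces the mixed model or sits beside it. One permitted reading is that the primary estimator changes after attrition by arm is known. On the reassuring branch, no specified analysis shows how far the 6-month result depends on MAR. The promise of unbiased estimates on the other branch is too strong, because joint and shared-parameter models rest on an assumed link between dropout and outcome that the data cannot verify.

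Outcome-related missingness is plausible here but not established. Protocol 8.3 says that stopping treatment can go with worsening or with improvement. That concerns stopping treatment, which is not the same as lacking a 6-month score.

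**Working it through.** **Inputs from the documents.** N = 350 allocated 1:1, so 175 per arm; target difference 0.37 SD of 6-month change; 80% power; 15% attrition at 6 months (SAP, Sample Size Calculation); 10-15% with no follow-up (Protocol Table 5). Two-sided 0.05 is stated for the interaction tests in Protocol 9.4.6 and assumed here for the primary test.

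**The plan's own figure.** Completers per arm: 175 × 0.85 = 148.75. SE = √(2/148.75) = 0.116 SD. Power for 0.37 SD = Φ(0.37/0.116 − 1.96) ≈ 89%, not the stated 80%. The difference is on the conservative side, and nothing below depends on it.

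**Can the two checks tell the mechanisms apart?** 3,000 trials of 350 were simulated per setting. Assumptions: correlation 0.6 between visits, true effect 0.37 SD, 15% of 6-month values missing per arm, and an MAR likelihood-type estimator. Under MAR, dropout depended on baseline only. Under MNAR it also depended on the unseen 6-month residual, in opposite directions by arm, with the baseline dependence set to give the same baseline imbalance.

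| | MAR | MNAR, moderate | MNAR, strong |
|---|---|---|---|
| Mean arm difference in missingness | 0.000 | 0.001 | 0.001 |
| Baseline standardized difference, missing vs observed | 0.49 | 0.49 | 0.49 |
| Bias of MAR estimator (SD) | −0.001 | −0.11 | −0.19 |

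The checks look the same and the bias does not. Opposite-direction dropout was chosen to make the point; no passage suggests it, and these bias sizes are not forecasts.

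**Size under a one-arm departure.** If missing participants supply no follow-up data, bias = fraction missing × (departure in arm 1 − departure in arm 2). The departure is the mean change of missing minus observed participants, in SD of change. The 0.25 and 0.5 SD departures are assumptions.

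- 15% missing: 0.15 × 0.25 = 0.0375 and 0.15 × 0.5 = 0.075 SD. Divided by 0.37, these are 10% and 20%. With SE 0.116, type I error is 6.2% and 9.9%.
- 10% missing: 0.025 and 0.05 SD, or 7% and 14% of 0.37. With SE = √(2/157.5) = 0.113, type I error is 5.6% and 7.3%.

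A random-intercept REML model was then fitted to simulated trials with visits at 0, 3, 6 and 12 months, correlation 0.5, 15% missing per arm, true difference 0 and 2,000 trials per cell. Site and depression covariates were omitted. Cells show bias in SD / type I error.

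| Missing visits | One arm, 0.25 | One arm, 0.5 | Equal, both arms | Opposite, 0.5 |
|---|---|---|---|---|
| All follow-up | 0.038 / 6.6% | 0.075 / 9.6% | 0.001 / 4.4% | 0.152 / 26.6% |
| Month 6 only; shift visible at 3 and 12 | 0.019 / 5.6% | 0.040 / 6.6% | 0.004 / 5.0% | 0.077 / 10.7% |
| Months 6 and 12; shift arises after 3 | 0.036 / 6.1% | 0.071 / 8.8% | −0.004 / 5.6% | 0.147 / 25.8% |
| Months 6 and 12; shift visible at 3 | 0.028 / 5.5% | 0.051 / 7.0% | −0.003 / 5.4% | 0.102 / 14.7% |

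At correlation 0.7 (1,000 trials), one-arm shifts of 0.25 and 0.5 gave 0.041 / 5.4% and 0.072 / 10.1% with all follow-up missing, and 0.017 / 4.6% and 0.031 / 5.5% with only month 6 missing.

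**The opposite error.** Let attrition be 20% vs 10% and depend only on arm, which is MAR (1,000 trials, months 6 and 12 missing). The mixed model has bias 0.007 SD (Monte Carlo SE 0.004) and type I error 5.1%. The arm comparison, if run as a 5% test (assumed), is positive in 75.9% of trials and the baseline comparison in 5.0%. For example, 35/175 vs 18/175 missing gives a chi-square p of 0.011.

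**The case against.** The strongest reply concerns size. Bias needs a departure that differs by arm; equal departures cancel. The arms share platform, coaching and assessment schedule, and no passage says that reasons for dropout differ between them. At 10% missing, or where other visits carry the information, type I error is close to nominal, and several cells cannot be told from 5%. Adjusting for baseline depression, which the SAP model does and the simulation does not, could shrink the departure further. At 15% missing, an observed difference of 0.37 SD would stay significant until one arm's missing participants departed by (0.37 − 0.227)/0.15 ≈ 0.95 SD, where 0.227 = 1.96 × 0.116. All of this stands. It limits the severity, although smaller observed effects would tip sooner.

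Second, the SAP does not say that an arm difference alone leads to an MNAR conclusion, and it sets no 5% test. No joint model was fitted to show what a false alarm would cost. That also stands: the 76% shows how readily a harmless pattern can look suspicious, not the resulting bias.

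Third, the analysis section names the mixed model without condition, so switching estimators is only one reading. That is fair, and the criticism is that the text leaves the fallback's role unsettled.

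The plan also prioritizes Pain Interference after treatment stops, requires repeated contact attempts, and at least names classes of MNAR model. These reduce the problem. They do not make the rule workable or supply an analysis that always runs.

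**Conclusion.** The concern holds. The classification rule cannot do what it is asked to do, the fallback's specification and role are open, and no MNAR sensitivity analysis of the treatment effect runs regardless of the classification. These conclusions follow from the text and from the definitions of MAR and MNAR, not from the simulations.

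The likely effect is modest. At 15% missing, a one-arm departure of 0.25 to 0.5 SD gives a bias of 0.04 to 0.075 SD when there is no follow-up, and 0.02 to 0.04 SD when only month 6 is missing and the shift shows at other visits. It is less at 10% missing and about zero under equal departures. The departure sizes and the correlations between visits are assumptions. A mixed model under MAR remains a reasonable primary analysis. The missing-data section should be corrected, but the design is not in doubt.

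**What to change.** In the SAP, under Handling of Missing Values:

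- State that the linear mixed model under MAR is the primary analysis whatever the attrition pattern.
- Keep the comparisons of attrition, baseline characteristics and reasons for dropout as description only.
- Pre-specify one MNAR sensitivity analysis of 6-month pain interference that is always run. Arm-specific delta-adjusted multiple imputation reporting the tipping point is one suitable choice; the imputation model and range of deltas should be written down before data by arm are seen.
- Label any joint or shared-parameter model supplementary, give its specification, and drop the claim that it yields unbiased estimates.
- Align Protocol 7.3 and 9.4.5.

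The cost is one SAP paragraph, matching Protocol text and a short extra analysis, with no new data.
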